### **Power Analysis**

We expect that treatment will result in a large effect and as such have set an anticipated Cohen's  $d$  as 0.95. Using this value along with standard study values of  $\alpha=0.05$  and  $\beta=0.80$  we calculated a minimum total study group requirement of 38 subjects with 19 subjects in each arm.

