### **Objectives**

The purpose of this study is to evaluate the efficacy of intravesicular Onabotulinumtoxin A injections for the treatment of interstitial cystitis (IC). Specifically, we hypothesize that trigonal Onabotulinumtoxin A injections is an effective treatment for IC and will result in more subjective and objective symptom relief than posterior wall Onabotulinumtoxin A injections.

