## **MATERIALS AND METHODS**

### **Design**

This is a single center, prospective, randomized clinical trial. Subjects will consist of patients referred to the urology clinic at Wake Forest University Baptist Medical Center with interstitial cystitis for whom conservative management/oral medications have failed and Onabotulinumtoxin A is recommended. These patients will all have undergone evaluation by [name]: an expert in the management of pelvic pain syndromes who sees >300 new patients each year.

Upon initial evaluation all subjects will undergo assessment including history taking and physical examination, urinalysis, subjective symptom assessment using self-reporting questionnaires, and objective symptom assessment using uroflowometry as well as the measurement of post void residuals.

After initial assessment subjects will be randomized into either the control or experimental cohorts. Subjects will receive a single dose of PO ciprofloxacin prior to injection unless culture or allergies dictate to use a different antibiotic. Each group will receive a total of 100 units of botox spread out among 10 separate injections. Subjects in the control group will have 10 injections made about the periphery of the trigone.

Subjects in the experimental cohort will receive a one time dose of 100 units of Onabotulinumtoxin A diluted in 10 mL of preservative free normal saline and injected in 1.0 mL boluses in a set pattern across the upper aspect of the trigone of the urinary bladder. Meanwhile, those subjects randomized to the control cohort will also receive a one time dose of Onabotulinumtoxin A using the same dilution and number of boluses, but boluses will be administered at random sites on the posterior bladder wall (excluding the trigone). Post –treatment, subjects will remain at the site for at least 30 minutes for observation and will demonstrate their ability to void before leaving. All procedures will be performed using the facilities of Wake Forest Baptist Medical Center.

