### **Sample Size and Randomization**

Each study arm will consist of 20 subjects for a total study population of 40. This number was chosen using estimates of symptom relief using our current patient population as reference.

Patients will be randomized to either the control or experimental cohort using a computer generated randomization table. Providers will not be aware of the subjects' cohort status until immediately prior to injection.

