### **Outcome Measure(s)**

The primary outcome will be a measurement of subjective patient pain using the Pelvic Pain and Urinary Urgency Frequency (PUF) questionnaire and the O'Leary-Sant Symptom and Problem Indexes. Patients will be asked to complete this questionnaire prior to treatment administration and at 30 and 90 days post treatment. The PUF and O'Leary Sant are previously validated tools that have been used by numerous researchers to evaluate pelvic pain. Secondary outcomes will be objective data as to patient performance in uroflowmetry as well as measurement of post void residuals. Patients will

again undergo these assessments prior to treatment and at 30 and 90 days post treatment to assess objective treatment effectiveness.

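### The power statement prints β=0.80 where its 19 per arm follows from power 0.80 (β=0.20), and its d of 0.95 is tied to no score, visit or quantified between-site difference

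*Combined protocol and SAP*

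**What the plan says.** Power Analysis opens with "We expect that treatment will result in a large effect and as such have set an anticipated" Cohen's d of 0.95. It gives α=0.05 and β=0.80 and concludes that "we calculated a minimum total study group requirement of 38 subjects with 19 subjects in each arm". It states neither the sidedness nor the test.

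Sample Size and Randomization sets the planned number: "Each study arm will consist of 20 subjects for a total study population of 40". On its source it says "This number was chosen using estimates of symptom relief using our current patient population as reference", with no figures. No attrition rate is given.

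Both arms are active. The Design section states that "Each group will receive a total of 100 units of botox spread out among 10 separate injections". The hypothesis in Objectives is that trigonal injection "will result in more subjective and objective symptom relief than posterior wall Onabotulinumtoxin A injections".

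Outcome Measure(s) states: "The primary outcome will be a measurement of subjective patient pain using the Pelvic Pain and Urinary Urgency Frequency (PUF) questionnaire", and the same sentence adds the O'Leary-Sant Symptom and Problem Indexes. On timing it says "Patients will be asked to complete this questionnaire prior to treatment administration and at 30 and 90 days post treatment". The Analytical Plan allows t-tests or ANOVA for continuous variables, and regression. It singles out no score or visit and has no multiplicity rule.

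**The concern.** There are two linked problems in the plan's only power statement.

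First, the error rate is wrong as written. A trial with β=0.80 would miss the assumed effect four times in five. Anyone who enters the printed inputs will not obtain 19 per arm.

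Second, the power cannot be attached to a comparison. A per-arm calculation concerns a difference between arms, here trigone versus posterior wall. The reason given for d is a large effect of treatment, and both arms are treated. The cited relief in current patients is unquantified and is not described as a difference between sites. Nor does the plan say whether 0.95 SD refers to PUF, the Symptom Index or the Problem Index, at day 30 or day 90.

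Two things are at stake. A non-significant result could be read as showing that site does not matter, when only a difference near 0.9 SD was likely to be detected. With several primary scores and visits and no rule for combining them, the chance of at least one false positive is above 5%.

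**Working it through.** **Inputs.** d=0.95, α=0.05, printed β=0.80 and 19 per arm come from Power Analysis; 20 per arm from Sample Size and Randomization; the t-test from the Analytical Plan. Two-sided α is an inference, tested in step 2.

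**1. Reproduce the stated figure.** For n per arm, the two-sample t-test has 2n−2 degrees of freedom and noncentrality d·√(n/2). Solving the two-sided power equation at d=0.95 and α=0.05:

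- power 0.80 (β=0.20): n=18.41, so 19 per arm and 38 in total, as stated;
- power 0.20 (β=0.80 as printed): n=3.89, so 4 per arm and 8 in total.

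The normal approximation gives the same picture. For power 0.80, n = 2(1.960+0.842)²/0.95² = 17.4, so 18 per arm. For power 0.20, n = 2(1.960−0.842)²/0.95² = 2.8, so 3 per arm.

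**2. Could another reading give 19?**

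| Reading | n per arm, exact t |
|---|---|
| Two-sided, power 0.80 | 18.41 → 19 |
| One-sided, power 0.80 | 14.43 → 15 |
| Two-sided, power 0.90 | 24.29 → 25 |
| One-sided, power 0.90 | 19.69 → 20 |

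One-sided power 0.90 gives 19 only by the normal approximation (18.98), and 0.90 appears nowhere in the plan. A paired before-and-after test at power 0.80 needs 11 subjects in all (10.77), so the stated number is a between-arm calculation. Two-sided power 0.80 is the natural reading.

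**3. What the planned size delivers.** These are for an unadjusted two-sided t-test, in SD units of the variable analysed. The 95% CI half-width is t(0.975, 2n−2)·√(2/n); for n=20 this is 2.024×√0.1 = 0.640.

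| Evaluable per arm | Power at d=0.95 | d with 80% power | CI half-width |
|---|---|---|---|
| 20 | 83.3% | 0.91 SD | 0.64 SD |
| 19 | 81.3% | 0.93 SD | 0.66 SD |
| 18 | 79.1% | 0.96 SD | 0.68 SD |

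The range of 18 to 20 evaluable is an assumption, because the plan gives no attrition figure. For illustration only, with assumed true differences and 20 per arm, power is 69% at 0.8 SD and 34% at 0.5 SD.

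**4. To which comparison does d belong?** Three named scores at two post-treatment visits give 3×2 = 6 comparisons if each is analysed separately. The count changes if the two O'Leary-Sant indexes are summed, or if both post-treatment values and changes from baseline are tested.

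**5. False-positive risk without a rule.** Six independent tests at 5% would give 1−0.95⁶ = 26%. These scores will be correlated. Simulation of six comparisons gives about 14% at an assumed common correlation of 0.8, and about 21% at 0.5. The plan gives no correlations.

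**The case against.** The strongest reply is that the β entry is a slip of notation. The plan calls its inputs standard values, 0.80 is the usual power, and 19 per arm follows from it. That is right: taken alone, this is an erratum with no effect on the design.

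It can also be said that every power figure depends on its effect size, and that the plan does not hide this, since it introduces d as expected and anticipated. The per-arm number together with the Objectives identifies the contrast as trigone versus posterior wall. The Background gives a reason for a site difference: most bladder nociceptor and parasympathetic fibres lie in the trigone. All of this stands. A reader might infer that the conditional nature of the 80% is concealed, or that a site difference is assumed without any reason. The documents support neither reading. What is missing is a size for that difference and the score and visit to which it applies.

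The detectable differences above also depend on the analysis. Baseline scores are collected, and the Analytical Plan permits ANOVA and regression. A baseline-adjusted analysis could detect a smaller difference in raw-score SD units. For that reason, any corrected text must name both the test and the SD.

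Finally, naming one primary comparison does more than correct a label, because it changes the outcome hierarchy. That is a real cost. It is justified because the power statement has no identifiable object without it.

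**Conclusion.** The point holds in a limited form. The printed β=0.80 should be power 0.80 (β=0.20). With that reading and a two-sided two-sample t-test, the plan's 38 subjects reproduce exactly, and N stays at 40. It would be wrong to infer that the trial has only 20% power or that its size was miscalculated: 20 evaluable per arm gives 83% power at d=0.95.

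The larger gap is that d=0.95 is not linked to a score, a visit or a quantified between-site difference, while three scores at two visits are primary with no multiplicity rule. This does not show that 0.95 is too large; the documents give no figure against which to judge it. Nor is six a fixed count of comparisons, because it depends on how the indexes and changes from baseline are handled.

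The conclusion rests on inferred two-sidedness, an unadjusted t-test, an assumed 18 to 20 evaluable per arm and, for the false-positive range, assumed correlations. The correction should be made. It requires no change of design.

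**What to change.** Keep N at 40.

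- **Power Analysis:** replace β=0.80 with *power=0.80 (β=0.20), two-sided*. Add: *d=0.95 is the assumed difference between trigonal and posterior-wall injection in [score] at [visit], in SD units of the variable analysed, for an unadjusted two-sample t-test. Under this test, 80% power corresponds to about 0.91 SD with 20 evaluable subjects per arm (0.93 with 19, 0.96 with 18; this evaluable range is an assumption).*
- **Outcome Measure(s):** name that same score and visit as the single primary outcome, and list the other scores and the other visit as secondary. The sponsor makes the choice before outcome data are examined by arm.
- **Analytical Plan:** add: *The between-arm difference in the primary outcome will be reported with its 95% confidence interval (expected half-width about 0.64 SD with 20 evaluable subjects per arm, same test and SD).*

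The cost is a few sentences in three sections, with no extra patients, visits or tests. The downside is that the sponsor must commit to one score and visit, and the remaining comparisons become secondary. The new text makes the assumption explicit but does not supply a basis for 0.95. If the estimates from current patients include a between-site figure, it should be added.

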### **Outcome Measure(s)**

The primary outcome will be a measurement of subjective patient pain using the Pelvic Pain and Urinary Urgency Frequency (PUF) questionnaire and the O'Leary-Sant Symptom and Problem Indexes. Patients will be asked to complete this questionnaire prior to treatment administration and at 30 and 90 days post treatment. The PUF and O'Leary Sant are previously validated tools that have been used by numerous researchers to evaluate pelvic pain. Secondary outcomes will be objective data as to patient performance in uroflowmetry as well as measurement of post void residuals. Patients will

again undergo these assessments prior to treatment and at 30 and 90 days post treatment to assess objective treatment effectiveness.

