After the procedure subjects will be scheduled for clinical follow-up at 2 weeks for a measurement of post void residual and adverse event collection. At the day 30 and 90 day follow-up visits patients will again undergo evaluation including collection of adverse events, concomitant medications, history taking and physical examination, urinalysis, subjective symptom assessment using self-reporting questionnaires, and objective symptom assessment using uroflowometry as well as the measurement of post void residuals. At day 45 and day 60 we will call to verify if patient has had any adverse events or changes in concomitant medications. We will then analyze the data generated by these follow-up visits to measure the efficacy of Onabotulinumtoxin A injections for interstitial cystitis as well as impact of injection location, if any.

Procedures, Tests and Evaluations	Screening and Baseline Study Day 0 in Clinic	Week 2 Clinic visit	Day 30 Clinic Visit	Day 45 Phone call	Day 60 Phone call	Day 90 Clinic Visit
	Day 0	Day 14 ±3	Day 30 ±3	Day 45 ±3	Day 60 ±3	Day 90 ±3
Informed Consent	X					
Medical History/Demographics	X					
Medical History verification		X	X			X
Concomitant Medications	X	X	X	X	X	X
Inclusion/Exclusion Verification	X					
Physical Examination (PE)	X		X			X
Uroflowometry	X		X			X
Pregnancy Test	X a					
Antibiotic dose	X					
Post-Treatment Observation and Void	X b					
Urinalysis/Urine Culture	X		X			X
Questionnaires—PUF, O’Leary-Sant	X		X			X
Bladder Post-void Residual	X	X	X			X
IP injections	X					
AEs	X	X	X	X	X	X

- a. For subjects who are of child-bearing potential
- b. Subjects will remain at site on Day 0 after treatment for at least 30 minutes for observation. Subjects must also demonstrate their ability to void before leaving.

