### **Subject selection criteria**

Written informed consent will be obtained from all subjects before enrollment. Once participants have been appropriately consented, the minimal amount of clinical data required will be abstracted from their electronic medical record. Other extracted information will include their past medical history, such as comorbidities, current medications, and any symptoms of IC they experience. Furthermore, physical exam findings, laboratory results, intra-operative findings, and pathology reports will be reviewed. Patients will complete questionnaires that have been well-established to assist in IC diagnosis and assessment of disease severity and response to treatment, and are part of routine clinical diagnosis and treatment. These include the O'Leary-Sant Interstitial and the Pelvic Pain and Urgency/Frequency Patient Symptom Scale (PUF). Each of these questionnaires are well established in the literature to help the urologist identify and treat patients with IC. Their scores on these questionnaires must >10 for either the ICSS or ICPI, and >10 on the PUF. Both the O'Leary/Sant questionnaire and PUF questionnaire ask about the voiding patterns and pain levels of IC patients.

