### **Analytical Plan**

Results will be analyzed initially using descriptive statistics. Comparison between groups will be done using chi square tests for proportions, and t-tests or ANOVA procedures for continuous variables. Regression analysis will be performed to identify independent outcome predictors. Other inferential statistical analysis will be conducted as appropriate.

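### The primary outcome spans three symptom scores at two visits with no deciding score, visit, form or success rule, while the sample size fits one unidentified test, so alpha 0.05 and 80% power are not jointly assured.

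*Combined protocol and SAP*

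**What the plan says.** Outcome Measure(s) defines the primary outcome in one sentence: "The primary outcome will be a measurement of subjective patient pain using the Pelvic Pain and Urinary Urgency Frequency (PUF) questionnaire and the" two O'Leary-Sant indexes (Symptom and Problem). On timing it says: "Patients will be asked to complete this questionnaire prior to treatment administration and at 30 and 90 days post treatment". That is three scores at two post-treatment visits.

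The other sections do not narrow this down:

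- **Design** (Materials and Methods): "We will then analyze the data generated by these follow-up visits to measure the efficacy of Onabotulinumtoxin A injections". The day 30 and day 90 visits are not ranked.
- **Subject selection criteria**: the Symptom Index, Problem Index and PUF appear as separate scores, but only as eligibility thresholds. The section also says that the O'Leary-Sant "questionnaire and PUF questionnaire ask about the voiding patterns and pain levels of IC patients", so calling the outcome pain does not pick out one score.
- **Analytical Plan**: "Comparison between groups will be done using chi square tests for proportions, and t-tests or ANOVA procedures for continuous variables". It adds regression for outcome predictors and then: "Other inferential statistical analysis will be conducted as appropriate". It names no primary test and no multiplicity adjustment.
- **Power Analysis**: from d = 0.95 and alpha 0.05, "we calculated a minimum total study group requirement of 38 subjects with 19 subjects in each arm".
- **Sample Size and Randomization**: 20 per arm, 40 in total. "This number was chosen using estimates of symptom relief using our current patient population as reference".

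Neither sample-size section ties d = 0.95 to a score, a visit or a form of endpoint.

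**The concern.** The Objectives section states a superiority hypothesis: trigonal injection gives more symptom relief than posterior wall injection. A claim of that kind needs a stated result that would establish it. Here the primary outcome can produce several between-arm results, and the plan does not say which one decides or how they combine.

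The stated alpha and power belong to a single test. Applied to several tests without a rule, their meaning depends on what counts as success. If any significant result is enough, the chance of a false claim rises above 0.05. If all must be significant, alpha is protected but power falls. Because the rule is open, the plan also leaves room to settle it after the data are seen. With 20 patients per arm, chance differences between scores and visits could easily matter to the conclusion.

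The form of the endpoint is open as well. The t-test and ANOVA options fit a post-treatment value or a change. The chi-square option would also allow a responder proportion. A Cohen's d of 0.95 does not mean the same thing for each.

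**Working it through.** **Inputs from the documents.** d = 0.95, alpha 0.05 and 19 per arm (Power Analysis); 20 per arm (Sample Size and Randomization); three scores and two post-treatment visits (Outcome Measure(s)). The Power Analysis prints beta = 0.80; the stated sample size reproduces only if this is read as power = 0.80.

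**Assumptions not in the documents.** Correlations between scores and between visits of 0.5, 0.7 or 0.9 in all nine combinations; normal data with equal SDs; for power, d = 0.95 on every score at every visit.

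**1. The plan's own figure.** For one two-sided two-sample t-test (noncentral t) at alpha 0.05 and power 0.80, d = 0.95 requires 18.41 per arm. Rounded up, this is 19 per arm and 38 in total, which matches. A one-sided test would need 14.43, rounded up to 15, which does not match. So the sample size corresponds to one two-sided test.

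**2. One named test at 20 per arm.** Noncentrality = 0.95 × √(20/2) = 3.004, with 38 degrees of freedom and critical value 2.024. Power is 0.833 (0.813 at 19 per arm), and the false-positive rate is 0.05.

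**3. Six separate tests (3 scores × 2 visits), each at two-sided 0.05.** If the tests were independent, the chance of at least one false positive would be 1 − 0.95⁶ = 0.265. Simulation over the correlation grid (60,000 trials per setting, 20 per arm) gives:

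| Success rule | Quantity | Range over the grid |
|---|---|---|
| Any of six | False-positive rate, no true difference | 0.12 (correlations 0.9/0.9) to 0.22 (0.5/0.5) |
| Any of six | Chance of at least one success, d = 0.95 | 0.93 to 0.99 |
| All six | Power, d = 0.95 | 0.50 (0.5/0.5) to 0.71 (0.9/0.9) |
| Bonferroni, 0.05/6 = 0.0083 | Power for each test | 0.59 |
| Bonferroni, 0.05/6 = 0.0083 | Chance of at least one adjusted success | 0.76 to 0.94 |

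The any-result rule has ample power but does not hold alpha. The all-six rule holds alpha (simulated rate at most 0.012) but not power. Bonferroni holds alpha, and whether it reaches 80% depends on what counts as success and on the correlations.

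**4. One composite of the three scores, averaged over both visits.** For standardised scores with score correlation s and visit correlation v, the variance of the average is [(1 + 2s)/3] × [(1 + v)/2].

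- s = v = 0.5: (2/3) × 0.75 = 0.50; effect = 0.95/√0.50 = 1.34; power at 20 per arm 0.985.
- s = v = 0.9: (2.8/3) × 0.95 = 0.887; effect = 0.95/√0.887 = 1.01; power 0.875.

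This is one test, so the false-positive rate stays at 0.05.

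**The case against.** The strongest reply is that the plan can be read so that nothing fails. Outcome Measure(s) speaks of a primary outcome in the singular, and the Analytical Plan allows ANOVA procedures, which could include one repeated-measures comparison of the arms. A single combined score averaged over visits would hold alpha at 0.05 with power above 0.80 (step 4). This stands as a limit on the point. It does not remove it, because the documents define no composite, no averaging and no repeated-measures test.

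A second reply is that the multiplicity figures rest on correlations and equal effects that the documents do not give. That is correct, and the ranges are illustrations. The direction is firmer: under an any-result rule, several tests at 0.05 that are not perfectly correlated give an overall rate above 0.05.

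Third, the Analytical Plan should not be described as prescribing unadjusted tests. It is silent on multiplicity, and its planned regression could include baseline scores. Silence still leaves the deciding test unnamed.

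A reader might go further and infer that one error rate must fail, that the sample size is miscalculated, or that the investigators mean to pick the best result afterwards. The documents support none of these. Some rules keep both properties, the 38 reproduces exactly, and an open rule is an opportunity for selection, not evidence of a plan to select.

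**Conclusion.** The concern holds in this form: alpha 0.05 and 80% power are not jointly assured for the primary outcome as defined, because the single test they describe is never identified. This much rests on the documents alone, together with the exact reproduction of 19 per arm.

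The size depends on the rule eventually used. At 20 per arm, six separate tests give a false-positive rate of about 0.12 to 0.22 if any counts, and power of about 0.50 to 0.71 if all must be significant. Those ranges assume correlations of 0.5 to 0.9 and, for power, d = 0.95 on every score and visit. One named test gives 0.05 and 0.83, provided d = 0.95 applies to it. The gap should be closed before outcomes are compared by arm, because until then the main claim of the trial has no defined error rate.

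**What to change.** **Outcome Measure(s) and Analytical Plan.** Before outcomes are compared by arm, name one primary comparison: one score or a defined composite, at one visit or averaged over both, with its form stated (post-treatment value, change or responder proportion). Test it at two-sided 0.05. Adjusting a continuous endpoint for its baseline value by ANCOVA is preferable, but a t-test on the named endpoint would also settle the multiplicity problem. Make the other scores and visits secondary. The sponsor should choose the score that best represents pain, since both questionnaires also cover voiding.

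**If several primaries are kept.** State the procedure (all must be significant, fixed order, or Holm) and the power it gives. For scale, 80% power for each of six Bonferroni-adjusted tests needs 28.6, so 29 per arm or 58 in total.

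**Power Analysis.** State which endpoint d = 0.95 refers to and its basis in the clinic population cited under Sample Size and Randomization. Restate the power if d is not supported for that endpoint.

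**Cost.** With one named primary the change is to wording only. Baseline, day 30 and day 90 scores are already scheduled, and 40 patients still give 0.83 power if d = 0.95 holds for the chosen endpoint. The downside is that a positive result on another score or visit cannot then carry the main claim.
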